## 5.2 Exclusion Criteria

1. Diabetes with any of the following:
  - a. Newly diagnosed within 12 weeks of screening
  - b. HbA1c  $\geq 9.5\%$  at Screening
  - c. Change in basal insulin regimen  $> 20\%$  within 3 months prior to Screening
  - d. For patients with type 1 diabetes: episode of diabetic ketoacidosis, or  $\geq 3$  episodes of severe hypoglycemia within 6 months prior to Screening
2. Acute coronary syndrome or stroke/TIA within 6 months prior to Screening
3. Major surgery, peripheral revascularization, or non-urgent percutaneous coronary intervention (PCI) within 3 months prior to Screening, or upcoming planned major surgery or major procedure (e.g., arterial revascularization) during the course of the study
4. Active pancreatitis within 4 weeks prior to Screening
5. Screening laboratory results as follows, or any other clinically significant abnormalities in screening laboratory values that would render a patient unsuitable for inclusion:
  - a. Alanine aminotransferase (ALT) or aspartate aminotransferase (AST)  $> 3.0 \times \text{ULN}$
  - b. Total bilirubin  $> 1.5 \text{ ULN}$  unless due to Gilbert's syndrome
  - c. Estimated GFR (eGFR)  $< 30 \text{ mL/min/1.73 m}^2$  [as determined by the CKD-EPI formula for creatinine clearance; (Levey et al. 2009)]
  - d. Urine protein/creatinine ratio (UPCR)  $\geq 500 \text{ mg/g}$
6. Uncontrolled arterial hypertension (BP  $> 180/100 \text{ mmHg}$ ) despite antihypertensive therapy
7. Uncontrolled hypothyroidism such as those with thyroid stimulating hormone (TSH)  $> 1.5 \times \text{ULN}$  and free thyroxine (T4)  $< \text{LLN}$ , clinical evidence of hypothyroidism, or thyroid hormone therapy that has not been stable for  $\geq 4$  weeks prior to Screening
8. Active infection requiring systemic antiviral or antimicrobial therapy that will not be completed prior to Study Day 1 or active Covid-19 infection with or without therapy that will not be resolved by Study Day 1
9. Active infection with human immunodeficiency virus (HIV), hepatitis C or hepatitis B (e.g., HBsAg positive) diagnosed by initial serological testing and confirmed with RNA testing, or prior treatment for hepatitis C. Patients at Screening who test positive by serology (for example, positive for Hepatitis C antibody), but negative by RNA may be allowed in consultation with the Sponsor Medical Monitor or designee

10. Malignancy within 5 years of Screening, except for non-melanoma skin cancers, cervical *in situ* carcinoma, breast ductal carcinoma *in situ*, or stage 1 prostate carcinoma that has been successfully treated. Patients with a history of other malignancies that have been treated with curative intent and which have no recurrence within 5 years may also be eligible if approved by the Sponsor Medical Monitor or designee
11. Hypersensitivity to the active substance or to any of the excipients (olezarsen or placebo)
12. Treatment with another investigational drug (non-oligonucleotide), biological agent, or device within 1 month of Screening, or 5 half-lives of investigational agent, whichever is longer
13. Previous treatment with an oligonucleotide (including small interfering ribonucleic acid [siRNA]) within 4 months of Screening or 5 half-lives, whichever is longer. This exclusion does not apply to vaccines
14. Concomitant medication/procedure restrictions:
  - a. Systemic corticosteroids or anabolic steroids within 6 weeks prior to Screening and during the study unless approved by the Sponsor Medical Monitor or designee
  - b. Use of bile acid resins such as colestipol, cholestyramine, or colesevelam within 4 weeks prior to Screening or planned during the study
  - c. Plasma apheresis within 4 weeks prior to Screening or planned during the study
  - d. Change in medications known to exacerbate hypertriglyceridemia such as certain beta blockers, thiazides, isotretinoin, oral antidiabetic medications, tamoxifen, estrogens or progestins within 4 weeks prior to Screening
  - e. Change in atypical antipsychotic medications (e.g., olanzapine and clozapine) within 3 months prior to Screening
15. Blood or plasma donation of 50 to 499 mL within 30 days of Screening or of > 499 mL within 60 days of Screening
16. Unwillingness to comply with study procedures, including follow-up, as specified by this protocol, or unwillingness to cooperate fully with the Investigator
17. Have any other conditions, including current or recent (< 1 year) alcohol abuse or other substance abuse, which, in the opinion of the Investigator would make the patient unsuitable for inclusion, or could interfere with the patient participating in or complete the study

## 6 STUDY PROCEDURES

### 6.1 Study Schedule

All required study procedures are outlined [Appendix A](#), [Appendix B](#), and [Appendix C](#).

#### 6.1.1 Screening

Written informed consent for the study will be obtained prior to the performance of any study-related procedures including screening procedures. An up to 8-week period is provided for completing screening assessments and determining patient eligibility for the study. Abnormal

screening results may be re-tested for determination of patient eligibility after consultation with the Sponsor Medical Monitor or designee. Patients may be re-screened in order to determine eligibility. However, re-screening will not be allowed if the patient screen-failed due to not meeting TG criteria.

During the Screening Period, patients will undergo a medical history and physical examination including vital signs, 12-lead ECG and have blood and urine samples taken for clinical laboratory testing. Patients will be screened for HIV, hepatitis B and hepatitis C.

As part of the Screening Period, patients will have at least 2 weeks of Diet/life-style Stabilization/Run-in Period, followed by an approximately 2 -week Qualification Period, during which final eligibility assessments will be performed. At the Qualification Visit, TGs will be measured.

Race & Ethnicity data will be collected as part of the demographic information for all screened patients during the Screening Period.

### **6.1.2 Treatment Period**

The Treatment Period is defined as the time between the first and the last dose of Study Drug plus 1 dosing interval (4 weeks) post-last dose. Patients will receive Study Drug administered by SC injection once every 4 weeks during Weeks 1-49 of the 53-week Treatment Period.

Collection and measurement of vital signs, physical examination results, ECGs, laboratory parameters ([Appendix B](#)), olezarsen plasma concentrations, ADA and biomarker samples, AEs and concomitant medication/procedure information will be performed according to the Schedule of Procedures in [Appendix A](#).

### **6.1.3 Post Treatment Follow-up Period**

After completion of the Week 53 visit assessments, patients will enter the 13-week Post-Treatment Follow-up Period.

## **6.2 Additional Study Assessments**

### **6.2.1 Laboratory Assessments**

Laboratory analyte samples will be collected throughout the study as per the Schedule of Procedures in [Appendix A](#). A list of these analytes is contained in [Appendix B](#).

Routine blood chemistry and lipid samples should be taken after fasting for at least 10 hours. Water and medications are not restricted during the fast, and the patient should ensure that they consume sufficient water in order to not become dehydrated.

Any confirmatory test, or test taken for safety reasons, may be taken at any time, irrespective of fasting status, but ideally no later than 7 days after the initial result is obtained.

If tests are uninterpretable (e.g., due to clumping, hemolysis or quantity not sufficient) or missing, a repeat blood or urine specimen should be re-drawn as soon as possible (ideally within 7 days).

Hematology samples will be collected monthly during the Treatment Period, and at every visit during the Follow-up Period. In the event that a hematology sample is unreportable (e.g., due to

hemolyzed or clumped blood samples), the patient's next scheduled dose should ideally not be administered until another sample is repeated and determined not to have met a PLT count stopping rule. The Investigator or designee will contact the patient to hold dosing until a new PLT count is obtained and reviewed. Use of home care provider or local laboratory (as described below) should be considered.

Investigators may, at their discretion, test specific laboratory parameters (except for those which must remain blinded e.g., lipid panel) which may be prone to clotting, clumping or hemolysis (e.g., hematology samples) at a local laboratory, in addition to the required central laboratory samples. In these instances, the local laboratory results should be recorded by the site into the electronic database. Assays which are blinded should not be locally tested and recorded into the database (e.g., lipid panel).

Blood and urine samples for renal function testing will also be collected monthly during the Treatment Period, and at every visit during the Follow-up Period, and sent to the central laboratory for analysis as per Section 8.5.2.

Liver chemistry testing will also be collected monthly during the Treatment Period, and at every visit during the Follow-up Period, and sent to the central laboratory for analysis as per Section 8.5.1.

All lab samples are to be sent to the central laboratory by overnight courier and processed. Lab alerts issued will indicate the applicable protocol section to facilitate review and will be immediately and simultaneously sent by email to the Investigator, the Sponsor and the CRO Medical Monitors, the Sponsor Drug Safety Physician, and the Clinical Trial Manager (CTM), and should be received by them within 2 days from sample collection. All lab sample results from local laboratories are received by the Study Center staff per the local laboratories' standard reporting time and should be entered as soon as possible (ideally within 1 week) into the electronic Case Report Form (eCRF) to inform the Sponsor and CRO study monitoring teams.

All PLT count results must be reviewed promptly (within 2 business days of receipt) by the Investigator, or designee, to ensure that the count has not met a dose interruption or stopping rule. Any case of PLT count reduction to levels below 50,000/mm^3 accompanied by a major bleeding (MB) event or clinically relevant non-major bleeding event (CRNMB), or PLT count of < 25,000/mm^3 independent of a MB or CRNMB event, is considered an AE of special interest (AESI) and must be reported in an expedited fashion to the Sponsor as per Section 9.3.4 and Section 9.4.1.

All liver and renal function tests must also be reviewed promptly (within 2 business days of receipt) by the Investigator, or designee, to ensure that the result has not met the stopping rule.

All lab alerts received, including those related to PLT, liver, or renal function monitoring/stopping rules, are also reviewed promptly by the Sponsor and the CRO Medical Monitors who will agree on actions to be taken according to the Medical Data Surveillance Plan.

Further information on safety monitoring and actions to be taken by the Study Investigator are provided in Section 8.5.

### **6.2.2 Physical Exams and Vital Signs**

Physical exams and vital signs will be performed as indicated in the Schedule of Procedures ([Appendix A](#)). Vital signs should include weight, blood pressure (BP), and pulse rate, and may also include respiratory rate and body temperature. Height will be measured at Screening.

### **6.2.3 Electrocardiography**

Electrocardiography will be conducted at Screening, Day 1 (prior to the first dose of Study Drug), and again at the end of the Treatment Period (Week 53) and the end of the Post-Treatment Follow-up Period as outlined in [Appendix A](#).

### **6.2.4 Pharmacokinetic Sampling**

Blood samples for the determination of plasma olezarsen concentrations will be collected prior to dosing on Day 1 and at various times throughout the treatment and Post-Treatment Follow-up Period as noted in the table in [Appendix A](#) and [Appendix C](#).

### **6.2.5 Pancreatitis Medical History**

Patient records will be reviewed for incidents of acute pancreatitis occurring up to 5 years prior to Screening and information relating to these events will be collected for independent adjudication.

## **6.3 Requirements on the Lifestyle of Patients**

### **6.3.1 Prevention of Pregnancy**

Every effort must be made to prevent pregnancy throughout the entire study. All male patients and women of childbearing potential must refrain from sperm/egg donation and either be abstinent† or practice highly effective contraception from the time of signing the informed consent form until at least 30 weeks after their last dose of Study Drug.

For the purposes of this study, females of childbearing potential are defined as any female who has experienced menarche, and who does not meet 1 of the following conditions:

- Postmenopausal: 12 months of spontaneous amenorrhea in females > 55 years of age or, in females ≤ 55 years, 12 months of spontaneous amenorrhea without an alternative medical cause and FSH levels in the postmenopausal range for the laboratory involved
- 6 weeks after surgical bilateral oophorectomy with or without hysterectomy
- Post-hysterectomy

For the purposes of the study, highly effective contraception is defined as follows:

For male patients:

- Highly effective male contraception includes a vasectomy with negative semen analysis at follow-up, surgically sterile via bilateral orchidectomy, or the non-pregnant female partner of childbearing potential uses a highly effective contraceptive method (defined below)

For female patients and female partners of male patients, highly effective contraception methods comprise:

- Surgical sterilization (e.g., bilateral tubal occlusion, hysterectomy, bilateral salpingectomy, bilateral oophorectomy), hormonal contraception associated with inhibition of ovulation (combined estrogen and progestogen containing, or progestogen-only), intrauterine contraception device or intrauterine hormone-releasing system (IUS), or the male partner uses highly effective contraceptive method (defined above). For female subjects in the trial, the vasectomised male partner with negative semen analysis at follow-up, should be the sole partner for that subject.

†**Note:** Abstinence (i.e., refraining from heterosexual intercourse throughout the duration of study participation) is only acceptable as true abstinence, i.e., when this is in line with the preferred and usual lifestyle of the patient. Periodic abstinence (e.g., calendar, ovulation, symptothermal, post-ovulation methods), declaration of abstinence for the duration of a trial and withdrawal are not acceptable methods of contraception.

**Note:** A female condom and a male condom should not be used together as friction between the 2 can result in either or both products failing.

**Note:** Male patients with partners that are pregnant must use condoms to ensure that the fetus is not exposed to the Study Drug.

### 6.3.2 Other Requirements

All patients will be required to fast for at least 10 hours before visits requiring fasted blood sampling. Water and medications are not restricted during the fast, and the patient should ensure that they consume sufficient water in order to not become dehydrated.

All patients will be encouraged to follow diet/life-style recommendations ([Appendix E](#)) during the study.

## 7 STUDY DRUG

### 7.1 Study Drug Description

Study Drug (ISIS 678354 or Placebo) characteristics are listed in [Table 1](#).

The Study Drug is contained in 2-mL stoppered glass vials. The Study Drug and its storage and preparation instructions will be provided by the Sponsor or designee. The Study Drug must be stored securely at 2-8 °Celsius and protected from light.

ISIS 678354 vials contain 100 mg/mL olezarsen in Water for Injection. Additionally, phosphate buffer and sodium chloride are added to control the pH of the solution and tonicity, respectively. The target pH is 7.4 and tonicity is within a physiologically acceptable range.

Placebo vials contain 0.9% sodium chloride in Water for Injection. Riboflavin is added for color similarity of placebo vials to olezarsen vials.

**Table 1: Study Drug Characteristics**

Study Drug	ISIS 678354	Placebo
Strength	100 mg/mL	Not Applicable
Volume/Formulation	0.8 mL solution per vial	0.8 mL solution per vial
Route of Administration	Subcutaneous	Subcutaneous

## **7.2 Packaging and Labeling**

The Sponsor will provide the Investigator with packaged Study Drug labeled in accordance with specific country regulatory requirements.

## **7.3 Study Drug Accountability**

The study staff is required to document the receipt, dispensing, and return/destruction of Study Drug supplies provided by the Sponsor according to Sponsor instruction and in accordance with institutional policy.

# **8 TREATMENT OF PATIENTS**

## **8.1 Study Drug Administration**

For each individual patient, in the 50 mg cohort (Cohort A), Study Drug will be administered SC as a single 0.5 mL injection once every 4 weeks during Weeks 1-49 for a total of 13 doses. For each individual patient in the 80 mg cohort (Cohort B), Study Drug will be administered SC as a single 0.8 mL injection once every 4 weeks during Weeks 1-49 for a total of 13 doses. Self-administration will be allowed after appropriate training of patient and/or caregiver.

Please refer to the Study Drug Manual provided by the Sponsor for more detailed instructions for Study Drug (ISIS 678354 or placebo) preparation, administration, and patient observation post-Study Drug administration.

## **8.2 Other Protocol-Required Drugs**

No other Study Drug treatments are required by the protocol.

## **8.3 Other Protocol-Required Treatment Procedures**

No other treatment procedures are required by the protocol.

## **8.4 Treatment Precautions**

No specific treatment precautions are required.

## 8.5 Safety Monitoring and Permanent Stopping Rules

Please refer also to the ‘Guidance for Investigator’ section of the Investigator’s Brochure.

- For the purposes of safety monitoring and permanent stopping rules Baseline is defined as the average of the Day 1 pre-dose assessment and the last measurement prior to Day 1
- In addition to the standard monitoring of clinical safety parameters, the following guidelines are provided for the monitoring of selected parameters chosen based on preclinical and clinical observations
- In case of discrepancy between the test results from 2 sources, such as between the central and local lab, safety-mandated action must be initiated based on the more critical (lower or higher, as relevant) of the 2 values

**Confirmation Guidance:** At any time during the study (Treatment or Post-Treatment Periods), the initial clinical laboratory results meeting the safety monitoring criteria presented below **must be confirmed** by performing measurements (ideally in the same laboratory that performed the initial measurement) on new specimens. All new specimen collections should take place as soon as possible (ideally within 3 days of the initial collection).

**Re-dosing Guidance:** In the event the initial laboratory result meets a stopping criterion, the results from the retest **must be available and reviewed by a Medical Monitor** prior to administration of the next dose of Study Drug (olezarsen or placebo). In general, patients who do not meet the stopping rules based upon retest may continue dosing. However, the Investigator and the Sponsor Medical Monitor (or designee) should confer as to at which dose Study Drug should be restarted, and whether additional close monitoring of the patient is appropriate. If any of the permanently stopping criteria described below are met, the patient will be permanently discontinued from further treatment with Study Drug (olezarsen or placebo), evaluated fully as outlined below and in consultation with the Sponsor Medical Monitor or designee, and will be followed up in accordance with Section 8.8. of the protocol.

The Investigator may interrupt or permanently discontinue study treatment for any medical reason including changes in clinical laboratory results.

### 8.5.1 Safety Monitoring and Permanent Stopping Rules for Liver Chemistry Tests

The following rules are adapted from the draft guidance for industry, “Drug-Induced Liver Injury: Premarketing Clinical Evaluation,” issued by the U.S. Department of Health and Human Services, Food and Drug Administration, July 2009. For a definition of Baseline, please refer to guidance above.

All patients will have liver chemistry tests monitored monthly during the Treatment Period. Upon completion of the study Treatment Period, liver chemistry tests should be monitored during the Post-Treatment Follow-Up Period as per visit schedule in [Appendix A](#).

All routine liver chemistry test results will be reviewed on an ongoing basis at the safety review by the Sponsor Medical Monitor.

All lab alerts for abnormal liver chemistry tests must be promptly reviewed by the Investigator (within 2 business days of receipt) and Medical Monitor(s) according to the Medical Data Surveillance Plan.

In the event of appearance of symptoms or signs of hepatic injury (jaundice, fatigue, nausea, vomiting, right upper quadrant pain or tenderness, fever, rash, abnormal bleeding or bruising, or eosinophilia  $> \text{ULN}$ ) liver enzymes (ALT/AST) and total bilirubin should be tested as soon as possible (ideally within 3 days). Testing at a lab that is local to the patient is permissible for this purpose.

In the event of an **ALT or AST measurement that is  $> 3 \times \text{ULN}$  (or the greater of  $2 \times \text{baseline value}$  or  $3 \times \text{ULN}$  if the baseline value was  $> \text{ULN}$ )** at any time during the study (Treatment or Post-Treatment Period), and the initial measurement(s) is confirmed (as described in Confirmation Guidance above) the following steps should be taken:

1. The Study Drug must be paused
2. Liver chemistry tests (ALT, AST, alkaline phosphatase [ALP], INR and total bilirubin) retested at least once weekly until ALT and AST levels become  $\leq 1.5 \times \text{ULN}$  or  $1.5 \times \text{baseline}$  if the baseline value was  $> \text{ULN}$
3. Further investigations into the cause of liver chemistry elevations should be performed. These may include the following evaluations\*:
  - a. Obtain a more detailed history of symptoms and prior and concurrent diseases
  - b. Obtain further history for concomitant drug use (including non-prescription medications, herbal and dietary supplement preparations), alcohol use, recreational drug use, and special diets
  - c. Obtain a history for exposure to environmental chemical agents and travel
  - d. Serology for viral hepatitis (HAV IgM, HBsAg, HCV antibody, cytomegalovirus (CMV) IgM, and EBV antibody panel)
  - e. Serology for autoimmune hepatitis (e.g., antinuclear antibody [ANA], and/ or anti-smooth muscle antibody [SMA])

\*Additional liver evaluations, including gastroenterology/hepatology consultations, hepatic CT or MRI scans, may be performed at the discretion of the Investigator, in consultation with the Sponsor Medical Monitor or designee.

4. Patients having alternative explanation for liver chemistry elevations may restart Study Drug at the original dose when ALT and AST levels become  $\leq 3 \times \text{ULN}$  (or below  $2 \times \text{baseline}$  if the baseline value was  $> \text{ULN}$ ) and following consultation with the Sponsor Medical Monitor or designee who must assess that alternative etiology is well supported as the likely cause.
5. Patients without alternative explanation for liver chemistry elevations but not yet meeting permanent Stopping Rules as described in bullet #6, must have Study Drug dose permanently reduced to 50 mg, if on an 80-mg dose (blinded olezarsen or placebo). Patients treated with 50-mg dose should remain on this dose.

6. Patients without alternative explanation for liver chemistry elevations and **meeting any of the following criteria must have Study Drug stopped permanently\*\***; values that are not confirmed due to failure to retest or missing lab values will be presumed confirmed:
- ALT or AST  $> 8 \times$  ULN, which is confirmed
  - ALT or AST  $> 5 \times$  ULN, which is confirmed and persists for  $\geq 2$  weeks
  - ALT or AST  $> 3 \times$  ULN (or the greater of  $2 \times$  baseline value or  $3 \times$  ULN if the baseline value was  $> \text{ULN}$ ), which is confirmed **and** total bilirubin  $> 2 \times$  ULN or INR  $> 1.5$
  - ALT or AST  $> 3 \times$  ULN (or the greater of  $2 \times$  baseline value or  $3 \times$  ULN if the baseline value was  $> \text{ULN}$ ), which is confirmed, **and** the new appearance (i.e., onset coincides with the changes in hepatic enzymes) of fatigue, nausea, vomiting, right upper quadrant pain or tenderness, fever, rash, and/or concomitant eosinophilia ( $> \text{ULN}$ )

\*\* The Investigator may decide to permanently stop Study Drug based on lesser changes in these parameters, taking into account all available and relevant data.

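### Protocol 8.5.1: for baseline ALT/AST above 2.5 × ULN, the pause trigger (2 × baseline) lies above the fixed 5 × ULN level of a permanent-stop rule

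*Combined protocol and SAP*

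**What the plan says.** **Pause.** Section 8.5.1 opens its numbered steps with an "ALT or AST measurement that is" above 3 × ULN or, if baseline was above ULN, above the greater of 2 × baseline and 3 × ULN. Once the value is confirmed, step 1 says "The Study Drug must be paused". Step 2 has liver tests "retested at least once weekly until ALT and AST levels become" 1.5 × ULN or lower (1.5 × baseline if baseline was above ULN). Step 3 adds: "Further investigations into the cause of liver chemistry elevations should be performed".

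**Restart.** Step 4 lets patients with an alternative explanation restart at 3 × ULN or lower, or below 2 × baseline if baseline was above ULN.

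**Permanent stop.** Step 6 covers patients without an alternative explanation and has four criteria. The second is ALT or AST above 5 × ULN, "which is confirmed and persists for" at least 2 weeks. That level and the 8 × ULN level of the first criterion are fixed multiples of ULN. The third and fourth (bilirubin or INR, and symptoms) repeat the baseline-adjusted expression of the trigger.

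**Who can enter.** Exclusion 5a in section 5.2 removes only patients with Screening ALT or AST above 3.0 × ULN. For the safety rules, section 8.5 says "Baseline is defined as the average of the Day 1 pre-dose assessment and the last measurement prior to Day 1".

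**Routine testing.** "All patients will have liver chemistry tests monitored monthly during the Treatment Period" (8.5.1). Appendix A places chemistry at the 4-weekly dosing visits, drawn before the dose, and not at Weeks 27 or 51.

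**The concern.** A pause level should be reached before a stop level. The other laboratory rules in section 8.5 follow that order. For renal function, the pause comes at an eGFR fall above 40%, UPCR above 1000 mg/g or UACR above 600 mg/g, and the stop at 50%, 2000 and 1200. For platelets, dosing pauses below 75K/mm³ and stops below 50K/mm³. The liver rules keep this order for most patients. They reverse it when baseline is high, because the trigger grows with baseline and the 5 × ULN stop does not.

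At stake is whether a mandatory hepatic stop works as written in patients who enter with raised enzymes. In the gap between 5 × ULN and 2 × baseline, 8.5.1 mandates no pause, no weekly retest and no step 3 work-up. Step 6 asks for two weeks' persistence and for the absence of another cause. The weekly retests and the search for a cause are what would establish these, and both hang on the trigger.

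**Working it through.** **Inputs, in multiples of ULN.** Let b be the safety baseline (mean of Day 1 and the last prior value, section 8.5).
- Pause trigger for b > 1: T(b) = max(2b, 3) (8.5.1, opening clause).
- Sustained-elevation stop level: 5, for at least 2 weeks (step 6, second criterion).
- Highest Screening value allowed: 3.0 (exclusion 5a).

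**Crossover.** T(b) > 5 exactly when 2b > 5, that is, b > 2.5.

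| Baseline b | Pause trigger T(b) | Stop level | Gap width T(b) − 5 |
|---|---|---|---|
| 2.0 | 4.0 | 5.0 | none |
| 2.5 | 5.0 | 5.0 | 0 |
| 2.6 | 5.2 | 5.0 | 0.2 |
| 2.8 | 5.6 | 5.0 | 0.6 |
| 3.0 | 6.0 | 5.0 | 1.0 |

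The 8 × ULN stop is not affected: the trigger passes it only if 2b > 8, that is, b > 4.0. The third and fourth criteria use the trigger expression itself. One of the four criteria is therefore out of order. The step 4 restart level is also 2b, so for these patients it lies between 5 and 6 × ULN, above the same stop level.

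**Who reaches b > 2.5.** The two averaged values must sum to more than 5.0 × ULN: for example, a run-in value of 3.0 with Day 1 above 2.0, or 2.5 with Day 1 above 2.5. The Screening limit does not bound the Day 1 value, so b could slightly exceed 3.0. I take 3.0 as the upper end.

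**What follows in the gap depends on how step 6 is read.**

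*Step 6 nested under the trigger.* All six steps follow the opening clause, so step 6 may apply only once the trigger is met. A patient with b = 3.0 who stays at 5.8 × ULN is above 5 but below 6.0. That patient is never paused and never reaches the mandatory stop. The effective stop level becomes the greater of 5 and 2b.

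*Step 6 standing alone.* The Re-dosing Guidance in 8.5 says a patient meeting any permanent criterion listed later is discontinued, which supports this reading. Take a dosing visit as day 0, with a value above 5 × ULN, and day 28 as the next dose:

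| | Above the trigger | In the gap |
|---|---|---|
| Confirmatory sample | ideally by day 3 | ideally by day 3 |
| Weekly retests before day 28 | days 7, 14, 21 (or 10, 17, 24 if counted from day 3) | none mandated |
| First sample at least 14 days after day 0 | day 14 to 17 | day 28 (routine) |
| Dosing | paused | next dose due day 28 |

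The delay is 28 − 14 = 14 days, or 28 − 17 = 11 days: roughly two weeks. The day 28 sample is drawn before the dose, but section 6.2.1 expects laboratory alerts within 2 days of collection, so the result may come as late as day 30. One dose can therefore be given before persistence is known.

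This reading assumes that the confirmation and re-dosing rules in 8.5 apply to a first value above 5 × ULN.

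**The case against.** The strongest reply is that several provisions already cover these patients. The Re-dosing Guidance requires a retest reviewed by a Medical Monitor before the next dose, and says the Investigator and Medical Monitor should confer on dose and on closer monitoring. The Investigator may interrupt or stop for any medical reason (8.5) and may stop on lesser changes (footnote to step 6). Step 6 presumes an untested value confirmed. Section 6.2.1 requires prompt review of every liver result. A baseline-relative trigger also tolerates fluctuation in patients with raised enzymes, and gap values are by definition at most 2 × baseline. A stop needing confirmation, two weeks and no other cause is not like-for-like with a pause threshold.

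Much of this stands, and it limits the harm. It does not restore the order of the thresholds. A retest at about day 3 cannot show two weeks' persistence. The presumption covers confirmation and not duration. After a retest that does not meet a stopping rule, the general default is to continue dosing. The remaining safeguards rest on judgement.

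Two stronger readings are tempting, and the documents support neither. A reader might infer that the protocol never requires the test needed to show persistence. It does: monthly chemistry supplies one at about day 28, so on the stand-alone reading the problem is delay. A reader might also infer that gap values plainly count toward permanent discontinuation. The opening clause of 8.5.1 and the Re-dosing Guidance point in different directions, so this is open.

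**Conclusion.** The inversion is real and exact: for baselines above 2.5 × ULN, the pause trigger exceeds the 5 × ULN stop level by up to 1.0 × ULN at a baseline of 3.0. On the nested reading, the mandatory stop for sustained elevation is out of reach while values stay between 5 × ULN and 2 × baseline. On the stand-alone reading, the cost is about two weeks' delay and possibly one dose.

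This is a minor correction to a safety rule. The documents do not give the number of patients with baseline above 2.5 × ULN; among about 152 it may be zero. Section 2.3.4 reports that no Phase 2 patient met a liver monitoring rule. Efficacy inference, power and type I error are not touched.

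Confidence in the arithmetic is high. Confidence in the practical consequence is moderate, because the wording is ambiguous and because alerts are handled under a Medical Data Surveillance Plan that was not available and may add retests. The Investigator's Brochure guidance, to which 8.5 refers, was not available either.

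**What to change.** Cap the pause trigger in 8.5.1 for patients with baseline above ULN at min(max(2 × baseline, 3 × ULN), 5 × ULN). No value can then exceed the 5 × ULN stop level without also meeting the trigger, whichever way step 6 is read. Apply the same 5 × ULN ceiling to the below-2 × baseline restart level in step 4, so that nobody restarts at a value that would set off a new pause. The cap does not collide with the end of weekly retesting in step 2, which is 1.5 × 3.0 = 4.5 × ULN at baseline 3.0.

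For consistency, the capped expression may also be used in the third and fourth criteria of step 6. Without that, a patient with baseline 3.0, ALT 5.5 × ULN and bilirubin above 2 × ULN would be paused but would not meet the third criterion. Such a patient does not meet it today either, so the cap alone leaves those criteria no weaker than now.

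The cost is one line and a matching phrase in step 4. Patients with baseline at or below 2.5 × ULN are unaffected. Above that, the pause comes at a smaller multiple of baseline: 5/2.6 = 1.92, 5/2.8 = 1.79 and 5/3.0 = 1.67, instead of 2. A very small group would have a few more pauses and weekly tests.
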